6.0 Measurements of Myocardial Blood Flow

Baseline absolute coronary flow, CFR and coronary flow capacity will be obtained for each major coronary artery territory [left anterior descending (LAD), left circumflex (LCx), right coronary (RCA)] using FDA-approved software HeartSee for each scan obtained. For the “infarct” group, region of interests will be drawn around the infarct territory where average and minimum resting myocardial blood flow will be determined for each scan.

7.0 Statistical Analysis

This is a measurement reliability study in a 2x2 factorial design. Study factors are infusion flow rate (20 or 50) at rest and stress. The linear nature of data acquisition takes about 45 minutes and yields five absolute values for each subject: three resting values and 2 stress values. The first 2 resting values and the 2 stress values condition are obtained in a cross-over fashion by infusion flow rate (infusion level assigned randomly for first resting scan and for first stress scan). The third resting value will be obtained at either a 20 or 50 infusion flow rate and will be used to determine precision (test-retest variability) against the same infusion profile obtained in the first two infusions.

Precision and variability will be determined for global, average quadrant, and individual pixel values of rest flow, stress flow and CFR. Standard summary statistical tests will be used. Applicable tests are 2-tailed, and $p < 0.05$ will be considered statistically significant. Linear regression will be reported between rest perfusion and rest pressure rate product (PRP). Paired or unpaired Student *t* test will be used to evaluate continuous variables where appropriate. The Pitman-Morgan *F* test will be used to test for differences in variability of perfusion between groups. To compare the histogram distribution between groups of stress perfusion and CFR for each of 1344 pixels as percentage of LV in color-

coded ranges of coronary flow capacity, we will use the Kolmogorov-Smirnov (KS) test for differences in histogram distribution.

8.0 Reporting of Adverse Events or Unanticipated Problems involving Risk to Participants or Others

Adverse events or unanticipated problems will be reported to [name] or [name] at [contact] and the Internal Review Board as directed by Ochsner Medical Center IRB rules and regulations.

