1.0 BACKGROUND

Positron Emission Tomography (PET) is the gold standard for non-invasive measurement of resting myocardial blood flow (rMBF) and stress myocardial blood flow (sMBF) (1,2). Measurements of MBF by PET using the radionuclides rubidium-82 (Rb-82), nitrogen-13 ammonia (N-13) or oxygen-15 labeled water have been well correlated with direct invasive measurements via doppler velocity and flow wires. The constellation of data has validated the upper limits of rMBF and sMBF in healthy, young volunteers as well as the lower limits in tissue with transmural myocardial infarctions (MI)(3-8). Furthermore, test-retest methodological precision of global PET myocardial perfusion by serial rest or stress PET minutes apart using a standard infusion bolus as measured of a 2D PET scanner is $\pm 10\%$.(9) Rb-82 and N-13 are the only FDA approved radiopharmaceuticals for myocardial perfusion imaging. Currently, Rb-82 is the preferred radiopharmaceutical at Ochsner. Given Rb-82's ultra-short half-life of 76 seconds, quantification of MBF poses significant challenges on contemporary 3D PET systems.

An estimated 95% of installed PET scanners are used mainly for whole-body ^{18}F -fluorodeoxyglucose (FDG) oncology applications. Therefore, these systems have not been designed historically with the performance specifications required to achieve accurate MBF quantification and to maintain high quality myocardial perfusion imaging. As opposed to most clinical PET applications that perform static imaging at some delayed time after the tracer biodistribution has stabilized, MBF quantification requires the acquisition of dynamic images starting immediately from time of tracer administration and including the biophysical distribution process.

During early time phase of the acquisition, almost all tracer activity is concentrated in a small bolus of the venous system contained within the scanner field of view resulting in very high detector count rates that risk saturating the photon detection and processing subsystems. In contrast, during late

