2.0 Rationale and Hypotheses

As perfusion metrics in the healthy volunteers, patients with risk factors and/or coronary artery disease and in tissue with transmural myocardial infarctions has been well defined(13) AND same day test-retest variability minutes apart using a bolus infusion is $\pm 10\%$ (9), we shall test 3 hypotheses.

The first hypothesis is repeated same day test-retest coefficient of variation (COV) of whole heart rMBF and sMBF acquired using a bolus on a modern 3D PET scanner falls within $\pm 10\%$. The second hypothesis is repeated same day test-retest COV of whole heart rMBF and sMBF acquired using a low flow profile on a modern 3D PET scanner falls within $\pm 10\%$. The third hypothesis is COV of whole heart rMBF and sMBF between bolus and low flow profile is $\pm 10\%$ where the bolus is considered the standard on a modern 3D PET scanner.

The above testing and hypotheses deal with precision of MBF measurements however does not address accuracy. Measuring accuracy of non-invasive MBF measurements poses significant challenges as a “gold standard” for comparison is not realistically achievable in a clinical setting. Invasive measurements would pose unnecessary risk for patients and non-invasive “gold standard” measurements would require a standardized “phantom pump” which is not available within industry. Instead, PET labs have traditionally relied on patient populations to determine accuracy. As such, this study will not test nor is it powered to answer questions regarding accuracy. As the PET camera is currently being installed and testing prior to a “clinical go-live” is preferable to ensure measured flow metrics are consistent with the literature, as part of quality assurance, testing of the above hypotheses will also allow us to make additional observations to:

- 1) Confirm healthy volunteers measured rMBF and sMBF fall within published ranges (rMBF 0.69-1.06 cc/min/g and sMBF >2.17cc/min/g) .(13)
- 2) Confirm clinical volunteers with risk factors and/or CAD measured rMBF and sMBF fall within published ranges (rMBF 0.50-1.10 cc/min/g and sMBF >1.09 to 2.17 cc/min/g).(13)

- 3) Confirm rMBF in regions of infarct in volunteers with prior large myocardial infarctions fall within published ranges (rMBF <0.45 cc/min/g with minimum <0.19 cc/min/g).(14)

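### Hypotheses 1 and 2 claim same-profile test-retest COV for stress flow, but the design repeats a profile only at rest

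*Combined protocol and SAP*

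**What the plan says.** Section 2.0 states three hypotheses, each covering rest and stress flow:

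- Hypothesis 1: "The first hypothesis is repeated same day test-retest coefficient of variation (COV) of whole heart rMBF and sMBF acquired using a bolus" is within ±10%.
- Hypothesis 2: "The second hypothesis is repeated same day test-retest COV of whole heart rMBF and sMBF acquired using a low flow profile" is within ±10%.
- Hypothesis 3: "The third hypothesis is COV of whole heart rMBF and sMBF between bolus and low flow profile" is ±10%, with the bolus as the standard.

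Because the comparison between profiles is a separate hypothesis, the first two can only mean repeats within one profile.

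Section 7.0 describes the data. The session "yields five absolute values for each subject: three resting values and 2 stress values". On the assignment of profiles: "The first 2 resting values and the 2 stress values condition are obtained in a cross-over fashion by infusion flow rate". The third resting scan is at either rate and "will be used to determine precision (test-retest variability) against the same infusion profile obtained in the first two infusions". The next paragraph nevertheless promises: "Precision and variability will be determined for global, average quadrant, and individual pixel values of rest flow, stress flow and CFR".

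**The concern.** Test-retest error for a given profile is estimated directly only from two scans under that profile and the same condition. Section 7.0 supplies such a pair at rest and none at stress. The one stress pair compares the two profiles, so its spread combines the repeat error of both with any profile effect.

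This matters because of the benchmark. Section 1.0 describes the ±10% figure as "test-retest methodological precision of global PET myocardial perfusion by serial rest or stress PET minutes apart using a standard infusion bolus". The trial has a like-for-like counterpart to that at rest but not at stress. As written, the report would have to leave the stress halves of two of its three hypotheses unanswered, present between-profile agreement as test-retest precision, or choose a model after the data are seen.

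**Working it through.** **Inputs.** Three rest and two stress scans per subject; rates 20 and 50; cross-over for the first two rest scans and for the two stress scans; third rest scan at either rate (Section 7.0). 85 enrolled, first 5 not analysed (Section 3.0), so 85 − 5 = 80. Participation ends after this PET session (Section 5.0), so no later visit adds a stress scan. The plan gives no sample-size or precision calculation to reproduce; its count of five values is 3 + 2.

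**Count of same-profile pairs.** There are 2 rest orders × 2 stress orders × 2 choices for the third rest scan = 8 possible sequences. Every sequence has exactly one same-profile rest pair and no same-profile stress pair.

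| Pairs over 80 subjects | Bolus (50) | Low flow (20) |
|---|---|---|
| Rest, same profile | about 40* | about 40* |
| Stress, same profile | 0 | 0 |

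*If the third scan splits evenly, which is an assumption; the plan gives no allocation. There are also 80 between-profile stress pairs.

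The rest repeat does allow two same-profile CFR values in a subject, but both use the same stress scan, so they carry no information on stress repeat error.

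**Can the between-profile stress pair stand in?** On the log scale let d = bolus − low flow. Then

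Var(d) = bolus error variance + low-flow error variance + subject-by-profile interaction variance,

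and the between-profile COV with the mean shift removed is SD(d)/√2. A value of 10% (Var(d) = 200 in squared percentage points) fits each of these:

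- 10% and 10%: 100 + 100 = 200
- 5% and 13.2%: 25 + 175 = 200
- 6% and 6% with an interaction SD of 11.3% on the difference: 36 + 36 + 128 = 200

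So one profile can miss ±10% while the pair appears to meet it, and both can meet it comfortably while the pair only just does.

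**Indirect route A: upper bound.** With independent errors and the mean shift removed, each profile's COV is at most SD(d) = 1.414 × the between-profile COV. To bound both at 10%, that COV must be at most 10/1.414 = 7.07%. With 79 df the upper end of a two-sided 95% interval multiplies the estimate by 1.184, so the observed value must be at most 7.07/1.184 = 5.97%. A one-sided 95% limit (factor 1.152) gives 6.1%. The shift must be removed first: 5% error in both profiles with a 12.2% mean shift gives √(25 + 12.2²/2) = 10.0% uncorrected, against 5.0% corrected.

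**Indirect route B: variance minus covariance.** If there is no subject-by-profile interaction, each profile's error variance equals its variance minus the covariance of the two stress values. In simulations of 80 subjects with a true COV of 10% in both profiles, 95% of estimates fell in these ranges. The between-subject CVs are assumptions, because the documents give none.

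| Between-subject CV | 95% of estimates |
|---|---|
| 15% | 6.5% to 12.8% |
| 20% | about 5.5% to 13.3% |
| 30% | below 2% to about 14.3% |

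In the last row about 2% of variance estimates are negative, so its lower end is unstable. For comparison, 40 direct same-profile pairs give 7.8% to 12.2%. Route B is also biased if its assumption fails: an independent 5% interaction per profile makes a true 10% read √(100 + 25) = 11.2%.

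**The case against.** The scan-sequence figure is missing from the available text and might be thought to show a stress repeat. Section 7.0 fixes the number and assignment of stress scans in words, so a figure showing one would contradict it.

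A stronger objection is that the planned data do carry information on stress error. Route A gives a bound. Pooling the two profiles, SD(d)/√2 from 80 pairs would lie between about 8.4% and 11.6% when the truth is 10% in both, which is tighter than 40 direct pairs. The Pitman-Morgan test, already in Section 7.0, could compare the variances of the two profiles. All of this stands, and it is why the conclusion is limited to the lack of a direct estimate. But the pooled figure needs equal errors and no interaction, which the plan does not state, and it gives one number where Hypotheses 1 and 2 need one per profile. Pitman-Morgan compares variances and does not estimate a COV.

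It can also be said that this is only a wording mismatch, that no hypothesis is named as primary, and that rest repeatability and Hypothesis 3 survive. That is fair on the cost of repair. It does not remove the problem that half of each of two hypotheses has neither a matching measurement nor a specified analysis.

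Finally, narrowing the hypotheses is not the only way to reconcile the sections: the plan could instead say where same-profile stress repeats come from. That is right, and the choice is the sponsor's.

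**Conclusion.** The concern holds. There are 0 of 80 same-profile stress pairs for bolus and 0 of 80 for low flow, and more subjects would not change that. The stress halves of Hypotheses 1 and 2, and test-retest precision of stress flow and CFR as promised in Section 7.0, have no direct estimate. This follows from the text of Sections 2.0 and 7.0 alone and needs no assumed figure.

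The indirect routes are secondary. Route A could support a bound of 10% if the shift-corrected between-profile stress COV came out at about 6.0% or less (two-sided 95% limit, independent errors). Route B is less precise than 40 direct pairs at every between-subject CV tried, and depends on there being no interaction.

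**What to change.** Reconcile Sections 2.0 and 7.0:

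1. Limit Hypotheses 1 and 2 to resting flow.
2. Report the stress pair, and the CFR derived from it, only under Hypothesis 3 as between-profile agreement.
3. In Section 7.0, reserve the term test-retest precision for rest flow.
4. Only if a statement on same-profile stress error is wanted, pre-specify one indirect route with its assumptions. Route A is an upper bound from the paired differences after removing the mean profile shift, assuming independent errors. Route B is variance minus covariance, assuming no subject-by-profile interaction, reported with its confidence interval and a rule for negative estimates.

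If the sponsor prefers to keep the stress parts as direct test-retest claims, Section 7.0 must state which scans supply the repeats; no scan schedule is proposed here.

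The cost of items 1 to 3 is rewording, with no extra scan or subject. The downside is a narrower claim: no same-profile stress COV for either profile unless an indirect route and its assumptions are adopted.

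### Profile order is randomised but no planned analysis uses it, so an average shift between consecutive scans would inflate the between-profile COV judged against 10%

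*Combined protocol and SAP*

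**What the plan says.** Section 7.0 (Statistical Analysis) describes five scans per volunteer, three at rest and two at stress. On the comparison of profiles it states: "The first 2 resting values and the 2 stress values condition are obtained in a cross-over fashion by infusion flow rate". Order is random, separately at rest and at stress: "infusion level assigned randomly for first resting scan and for first stress scan". The third rest scan repeats one of the two profiles and always comes after the scan it is compared with. At stress each profile is scanned once.

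The analyses listed are summary statistics, a paired or unpaired t test that "will be used to evaluate continuous variables where appropriate", a Pitman-Morgan "test will be used to test for differences in variability of perfusion between groups", a Kolmogorov-Smirnov comparison of histograms, and a reported regression of rest perfusion on pressure rate product. No period, sequence or scan-position term is mentioned.

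Section 2.0 sets the target: "The third hypothesis is COV of whole heart rMBF and sMBF between bolus and low flow profile" is to lie within 10%. That is the same size as the same-day test-retest variability cited there and in Section 1.0. No COV formula is given.

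**The concern.** Hypothesis 3 concerns spread, not a mean. In a cross-over with random order, a constant shift from the first to the second scan cancels on average from the profile contrast. It does not cancel from the variability of the paired differences, because volunteers scanned bolus-first carry it with one sign and those scanned low-flow-first with the other. A COV built from those pairs therefore counts drift during the session as disagreement between profiles.

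If drift were large enough, hypothesis 3 could fail although the profiles agree. At stress there is no same-profile repeat, so the randomised order is the only feature of the design that can separate average drift from profile disagreement.

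**Working it through.** **Inputs from the documents.** Limit 10% (Section 2.0). Random order at rest and at stress (Section 7.0). Analysed volunteers: 85 - 5 = 80 = 40 + 20 + 20 (Sections 3.0 and 4.0). The plan has no sample-size or precision figure to reproduce.

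**Assumptions.** s is the drift-free between-profile COV, taken as 8% or 9%. d is the mean second-minus-first shift as a percentage of mean flow, taken as 3% to 10%. There is no true profile difference. Because the COV is undefined, two common definitions are tried, with s on each definition's own scale.

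**Formulas.** Each bolus-minus-low-flow difference is +d or -d plus error.
- Within-pair COV, root mean square: the error variance of a difference is 2s², so COV² = (2s² + d²)/2 and COV = sqrt(s² + d²/2).
- SD of paired percent differences: sqrt(s² + d²).

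| Drift-free COV | d | Within-pair COV | SD of differences |
|---|---|---|---|
| 8% | 3% | 8.3% | 8.5% |
| 8% | 5% | 8.75% | 9.4% |
| 8% | 10% | 10.7% | 12.8% |
| 9% | 3% | 9.2% | 9.5% |
| 9% | 5% | 9.7% | 10.3% |
| 9% | 10% | 11.4% | 13.5% |

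**Drift needed to reach 10%.**
- Within-pair: sqrt(2(100 - 64)) = 8.5% from 8%; sqrt(2(100 - 81)) = 6.2% from 9%.
- SD of differences: sqrt(100 - 64) = 6.0% from 8%; sqrt(100 - 81) = 4.4% from 9%.

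**Simulation** (10,000 runs, n = 80, d = 8%, within-pair definition). With a drift-free 8%, the chance that the observed COV exceeds 10% is 0.38 without a scan-order term and 0.001 with one. With a drift-free 9% it is 0.78 and 0.08. The mean profile contrast averaged about zero throughout, as expected under random order.

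**Interval for the mean contrast** (n = 80, s = 8%, t with 79 degrees of freedom = 1.99). The half-width is 1.99 × sqrt(2 × 64)/sqrt(80) = 2.5 points without drift, and 1.99 × sqrt(128 + 100)/sqrt(80) = 3.4 points at d = 10%. A period-adjusted analysis recovers this loss.

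**The case against.** The strongest reply is that no drift is documented. Under the within-pair definition, 5% of drift reverses neither example, and the 10% that reverses both is a uniform shift as large as the whole cited test-retest variability. This stands, and it makes the point conditional.

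Second, the cited 10% benchmark comes from serial scans and may itself contain drift. A drift-free COV would then be set against a limit that is not drift-free. This also stands, and is a reason to show both COVs.

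Third, the plan is silent on order; it does not commit to ignoring it. An unpaired t test of within-volunteer differences between the two order groups is a standard period-adjusted cross-over analysis, and Section 7.0 allows unpaired tests. But that adjusts the mean contrast, not the COV. The regression on pressure rate product covers rest only and is not said to adjust anything.

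A reader might also infer that chance imbalance of order within a group of 20 biases the profile contrast. The documents do not support this as a separate fault. Hypothesis 3 is not stated by group, and Section 5.0 refers to an attached scan protocol that may say more on allocation. Under random order such imbalance is sampling error that the paired interval already covers. Its SD is d/sqrt(n): 0.11d over 80 volunteers and 0.22d over 20.

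**Conclusion.** The omission is real and worth correcting, but its effect depends on a drift the documents do not quantify. A mean shift of about 6.2% to 8.5% (within-pair COV) or 4.4% to 6.0% (SD of differences) would take a drift-free 9% to 8% up to the limit. At 3% of drift the change is at most about half a point.

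A reader might infer that hypothesis 3 will be wrongly rejected, or that the mean bolus-versus-low-flow contrast is biased. Neither follows: the first needs a drift size that is nowhere given, and randomised order protects the second. Nor is drift the only threat to the limit. If the drift-free COV were itself 10%, the limit would be missed about half the time with no drift at all.

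**What to change.** 1. State the COV formula.
2. For hypothesis 3, analyse log whole-heart flow with volunteer, infusion profile and scan position, separately at rest (scans 1 and 2 only) and at stress (the two stress scans). Report the profile ratio with its period-adjusted 95% CI, and the scan-position shift.
3. Compute the between-profile COV after removing only the mean scan-position shift. Show it beside the unadjusted COV, and name in advance which of the two is judged against 10%.
4. Keep any mean profile difference in that COV. The residual SD of a model with profile as a fixed effect would drop it: with 8% error and low flow reading 15% off, the within-pair COV is sqrt(64 + 225/2) = 13.3%, while the residual stays near 8% and would pass. Leave the third rest scan out of this calculation, because it would mix same-profile retest error into the between-profile figure.
5. For the rest test-retest COV, where the repeat always comes last, report the mean third-minus-earlier shift beside the COV.

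The cost is a few sentences, no new scans and one degree of freedom per condition. The adjustment removes average drift only; drift specific to a volunteer stays in the COV.

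### Section 7.0 promises test-retest precision for CFR, but with one stress scan per profile the only same-profile CFR pair shares its stress value and repeats the rest-flow COV

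*Combined protocol and SAP*

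**What the plan says.** Section 7.0 says that the session "yields five absolute values for each subject: three resting values and 2 stress values". On how these are assigned, it says: "The first 2 resting values and the 2 stress values condition are obtained in a cross-over fashion by infusion flow rate". Each profile therefore has one of the first two rest scans and one stress scan.

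The only repeat at the same profile is the last rest scan: "The third resting value will be obtained at either a 20 or 50 infusion flow rate and will be used to determine precision". In parentheses the plan equates this with test-retest variability, and the comparison is with the earlier scan at that profile. This is where Section 7.0 says what it means by precision.

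The next paragraph extends the promise: "Precision and variability will be determined for global, average quadrant, and individual pixel values of rest flow, stress flow and CFR". Section 6.0 adds that CFR is to be produced for every scan. Neither section says which rest scan is paired with which stress scan to form a CFR, and Section 7.0 gives no formula for the COV.

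The 10% limits are in Section 2.0. They cover whole-heart rest and stress flow ("The first hypothesis is repeated same day test-retest coefficient of variation (COV) of whole heart rMBF and sMBF acquired using a bolus", "The second hypothesis is repeated same day test-retest COV of whole heart rMBF and sMBF acquired using a low flow profile" and "The third hypothesis is COV of whole heart rMBF and sMBF between bolus and low flow profile"). None of the three hypotheses names CFR.

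**The concern.** CFR, in its usual sense, is stress flow divided by rest flow, so the repeat error of a CFR should reflect error in both scans. A same-profile CFR repeat needs two rest scans and two stress scans at one profile. The design supplies two rest scans and one stress scan at the repeated profile, and one of each at the other profile.

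The gap is easy to miss. For stress flow no same-profile pair exists, so an analyst sees at once that nothing can be computed. For CFR two values can be formed at the repeated profile, and the analysis runs and returns a plausible number. That number is the repeatability of rest flow under another name. Section 7.0 describes the trial as a reliability study, so a precision figure that omits one of its two error sources would misdescribe one of the study's stated outputs.

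**Working it through.** **Inputs from the documents.** Three rest and two stress scans per volunteer, one stress scan per profile, and one rest repeat at one profile (Section 7.0). Prior precision of ±10% for serial rest or serial stress scans (Section 1.0), used here as the COV of a single rest or stress measurement. The plan states no CFR precision figure, so there is none to reproduce.

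**Assumptions.** The correlation rho between the rest and stress errors within one CFR is not given, so it is varied below. COVs other than 10% are illustrative.

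**Step 1: cancellation.** Let R1 be whichever of the first two rest scans used the repeated profile, R3 the third rest scan, and S the single stress scan at that profile. For two measurements a and b, COV = √2 × |a − b| / (a + b). Then

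|S/R1 − S/R3| / (S/R1 + S/R3) = |R3 − R1| / (R3 + R1).

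This is algebra and needs no distributional assumption. Example with assumed values S = 2.8, R1 = 0.80, R3 = 0.92:

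- Rest: √2 × 0.12 / 1.72 = 9.87%.
- CFR (3.500 and 3.043): √2 × 0.4565 / 6.5435 = 9.87%.

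The identity holds for a single global, quadrant or pixel ratio. If global CFR is instead the mean of 1344 pixel ratios, simulation gave 10.16% for both. If the COV is based on the SD of differences over the grand mean, simulation gave 10.1% for rest, 10.5% for the shared-stress CFR and 14.8% for a CFR with its own stress scan each time.

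**Step 2: what a full CFR repeat would show.** With CVr and CVs the rest and stress COVs,

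CV(CFR) = √(CVr² + CVs² − 2 × rho × CVr × CVs).

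With independent errors (rho = 0):

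| Rest COV | Stress COV | Shared-stress pair | Full CFR repeat |
|---|---|---|---|
| 10% | 10% | 10% | √(0.0100 + 0.0100) = 14.1% |
| 8% | 12% | 8% | √(0.0064 + 0.0144) = 14.4% |
| 10% | 5% | 10% | √(0.0100 + 0.0025) = 11.2% |

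Simulation with log-normal errors gave 14.0%, 14.2% and 11.1% for the last column. In the first row the shared-stress figure is 1 − 10/14.1 = 29% too low. With both COVs between 5% and 15%, the ratio of shared-stress to full figure runs from 0.32 (rest 5%, stress 15%) to 0.95 (rest 15%, stress 5%).

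**Step 3: dependence on rho.** At 10% for both:

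| rho | 0 | 0.25 | 0.5 | 0.75 |
|---|---|---|---|---|
| Full CFR repeat | 14.1% | 12.2% | 10.0% | 7.1% |
| Shared-stress pair | 10% | 10% | 10% | 10% |

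The two are equal when CVs = 2 × rho × CVr, that is rho = CVs / (2 × CVr), or 0.5 at equal COVs. Below that the shared-stress figure is too small; above it, too large.

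**Step 4: the pair that can be used.** S20/R20 against S50/R50, with the first two rest scans, uses four separate scans. With independent errors its within-subject variance is about (v20 + v50)/2 + d²/2, where v20 and v50 are the squared CFR COVs of the two profiles and d is the relative profile difference. At 10% for all scans, simulation gave 14.0% for d = 0, 14.4% for d = 5% and 15.5% for d = 10%.

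This is an average over the two profiles. If one had a CFR COV of 18% and the other 10%, with d = 0, the result would be √((0.0324 + 0.0100)/2) = 14.6%, below the 18% of the noisier profile.

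**The case against.** The strongest objection is that no section instructs the analyst to divide one stress value by two rest values. Section 7.0 gives the third rest scan a rest-against-rest use, and the CFR sentence does not repeat the words about the same profile. The between-profile pair could satisfy that sentence, so this may be only an unstated pairing rule. The pairing might also be set out in the attached protocol or in a figure not visible in the text available.

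Part of this stands: the flawed pairing is not prescribed. But Section 7.0 has just equated precision with same-profile test-retest variability when it promises precision for CFR. The shared-stress pair is the only one the five scans allow in that sense. An attachment could define pairing but could not supply a second stress scan, because the text fixes five values. The promised property is one that the design lacks.

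A reader might also infer three stronger things that the documents do not support:

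- **That CFR precision is bound to be understated.** Step 3 shows that this depends on a correlation the documents do not give. Independence is a natural assumption for separate acquisitions, but it remains an assumption.
- **That CFR could wrongly pass a 10% test.** Section 2.0 sets no such test for CFR.
- **That the flow-capacity comparison is distorted.** Section 7.0 compares those histograms with a Kolmogorov-Smirnov test, which does not use the CFR COV.

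**Conclusion.** The point holds. Same-profile test-retest precision of CFR cannot be estimated from the planned scans. The figure that can be computed in its place equals the rest-flow COV, exactly for the two-measurement COV and nearly so under the other definitions tried, and carries no stress-scan error. That conclusion rests only on the scan scheme in Section 7.0 and on CFR being a ratio.

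The size rests on assumptions: about 10% shown against about 14% true with independent 10% errors, and the opposite direction at equal COVs once the correlation exceeds 0.5. Whatever the direction, the figure is not an estimate of CFR repeatability. The weight is moderate: CFR is a named output of a reliability study, but no hypothesis or limit depends on it. The lack of a same-profile stress repeat also bears on the stress-flow parts of the first two hypotheses; that is a separate matter.

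**What to change.** In Section 7.0:

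1. Remove the claim of same-profile precision for CFR.
2. State that no CFR pair will be formed from a shared stress scan.
3. State that the third rest scan is used for rest-flow precision only.
4. Define the pairing and report CFR as between-profile agreement, S20/R20 against S50/R50, using the first two rest scans.
5. Label that result as combining the average repeat error of the two profiles with any profile difference. Do not describe it as an upper bound on either profile's own error, for the reason in Step 4.
6. Give the COV formula.

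The cost is SAP wording only: no new scans or participants. The downside is that no profile-specific CFR precision is reported, and the CFR figure will probably look less favourable. Profile-specific CFR precision would need a second stress scan at the same profile, a design decision for the sponsor that is not proposed here.
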